Data at pre- and post-surveys will be collected on tablets using surveys programmed in REDCap. Computerized assessments are transferred electronically to UTHealth on a weekly basis. We have used similar protocols with our previous homeless youth studies with success. REDCap is a well-tested computerized survey program, our staff is trained in REDCap surveys, and our extensive experience should reduce implementation, data management, and design problems. Participants entering data will be able to interrupt and resume sections in mid-course, review previously entered data, and back up to change prior entries. The quality of the data on these programs is enhanced, as REDCap will provide immediate feedback to the participant if unexpected data are entered. Only data analysis personnel connected with the study will have access to data files. Those files will be de-identified and not contain any identifying information.

Paper Study Documents. A hard copy of the participant consent and tracking forms will be saved in a secured and locked filing cabinet at the UTHealth School of Nursing for seven years. All study related forms, surveys, and data will be destroyed by shredding after seven years. In order to assure security of the data, we will make weekly backup copies of the REDCap data set. These copies will be stored in a secure area physically separate from the data management and analysis sections of the main project site.

Phone Data Loss Prevention. Participants will be provided with a study-issued smart phone to facilitate participant follow-up and access to pre-programmed homeless youth resources. In our previous study, we had a phone loss or damage rate of 12%. If a phone is lost, it will be remotely wiped. One replacement phone will be provided to each participant in the event of a lost, stolen, or damaged phone. No data will be collected or stored on the phones. Phones will only be used to contact participants to schedule follow-up appointments.

Data Protection during Data Sharing. The privacy and confidentiality of research participants will be protected at all times, including qualitative (audio files) and quantitative (surveys) data collection, analysis, storage, and preparing public-use data sets. Therefore, data to be released will be de-identified, which will ensure that linkages to individual research participants cannot be made. Data will be de-identified per HIPAA definitions; all Personal Health Information (PHI) will be removed. All data will be formatted to allow for maximum accessibility using non-proprietary, unencrypted, uncompressed software. Whenever possible, we will use standard, widely used file formats for storing the data produced through study activities, e.g., PDF for text, Excel, SAS or ASCII format for electronic data.

Focus Group Discussion Data. A total of 56 homeless youth 18-25 years old will be recruited to participate in focus group discussions (FGDs). FGDs will be planned around already scheduled events where youth would be receiving meals or services at CHT. Private rooms such as the library or conference room will be used to minimize distractions. These areas are within CHT to ease accessibility to the youth and are sufficiently private to prevent nonparticipants from overhearing the conversations. After providing written consent, each youth will complete a brief survey to assess the demographics of the focus group sample. Focus groups will comprise 6-8 youth each and last approximately 1-1.5 hours. FGDs will be recorded and professionally transcribed verbatim. The research assistant (RA) will take

copious field notes during all of the FGDs to be used in the data analysis. Participants will receive a \$20 gift card for a local grocery store for participating in the FGDs.

Example Focus Group Guide. While the focus group guide will be finalized during YR-1 with the assistance of the HYWG and expert advisory panel, we anticipate to query the participants about: 1) what they know or have heard about mindfulness and other contemplative practices, 2) lived experiences while homeless, 3) sources of stress, 4) stress management strategies, 5) emotion regulation strategies, and 6) barriers and facilitators to session attendance. We also anticipate asking general open ended questions about 6) what they propose as session content, delivery methods, session length and spacing, activities, and group discussion topics, 7) number and types of questions to include in the baseline, pre-post session, and initial follow-up survey, and 8) thoughts on the intervention sessions including content, length, delivery mode, frequency/spacing, perceived impact.

Homeless Youth Working Group Session. In these working sessions we will present session materials and delivery modality examples and query participants about 1) session content, delivery methods, session length and spacing, activities, and group discussion topics, 2) number and types of questions asked in the baseline, pre-post session, and initial follow-up survey, 3) what they thought of draft intervention session materials (e.g., content, length, delivery mode, frequency/spacing, perceived impact) when demonstrated, 4) usefulness of the practice tools (e.g., if they used it and for what), 5) utilization of the study-issued phone to facilitate communication and follow-up planning, and 6) any other comments the participant has about the intervention or study procedures.

Key Informant Interviews. Using a loosely structured conversational style interview guide,¹²² we will conduct key informant interviews with 12 YEH service providers to gain additional perspective on how the proposed adaptations, materials, and activities in the sessions meet the needs of YEH and elicit suggestions to assure the materials are trauma-informed and youth-friendly. Interviews will last approximately 30-45 minutes, be audio recorded, and transcribed verbatim for analysis. Participants will receive a \$20 gift card for a local grocery store for participating in the interview.

Example Key Informant Interview Guide. While the key information interview guide will be finalized during YR-1 with the assistance of the HYWG and advisory panel, we anticipate to query participants about: 1) what they propose as session content, delivery methods, session length and spacing, activities, and group discussion topics, 2) number and types of questions asked in the baseline, pre-post session, and initial follow-up survey, 3) thoughts on the intervention sessions (e.g., content, length, delivery mode, frequency/spacing, perceived impact) when demonstrated, 4) usefulness of the practice tools proposed (e.g., if they used it and for what), 5) utilization of the study-issued phone to facilitate communication and follow-up planning, and 6) any other comments the participant has about the intervention or study procedures.

Expert Advisory Panel. This group comprises 8 YEH service providers recruited from the Homeless Youth Network and 2 YEH. The group will be convened by phone or in-person every other month for 1-hour during the course of the study to provide input on intervention development, implementation, evaluation, and study protocols.

Plan, Do, Study, Act Field Notes. A Homeless Youth Working Group (HYWG) comprising up to 10 participants will be asked to participate in iterative intervention pre-pilot sessions. Multiple iterative sessions will be conducted to finalize *CALM* session content (materials and activities) with homeless youth (n=10) using pre-post surveys, exit interviews, and instant feedback processes. During this phase

of development, participants will debrief after each activity (e.g., didactic session, practice, video) using open-ended qualitative (e.g., Tell us what you thought of this activity) and quantitative (e.g., On a scale of 1-10, how helpful was the last activity?) responses to assess perceived acceptability, relatability, and perception of the impact the activity would have. At the end of each session, there will be a group interview style debriefing to assess general impressions of the activities and suggested modifications. This iterative Plan, Do, Study, and Act⁹ process will allow the team to determine session content preferences including approach, method, length, tone, and verbiage. Message modifications will be made using iterative field testing with the HYWG until session material and activities are rated as acceptable and relatable with high perceived post-session behavioral action.

Baseline and Follow-up Survey Data. During the pilot phase, a baseline and follow-up survey will be administered at immediate post and 3 months post intervention and will take approximately 45 minutes each to complete. We will finalize the pre- and post-surveys during the development phase with the assistance of the Homeless Youth Working Group (HYWG) feedback. We anticipate including items to assess demographics (e.g., homelessness, historical factors, race/ethnicity, sexual orientation, gender identity) and behavioral outcomes. Additionally, the post-surveys will contain items measuring usability, mediating factors, and risk behaviors. To assess feasibility, we will calculate the number of eligible youth approached, participation refusal rate with reason for refusal, the number of sessions attended, follow-up survey response rates, and successful tracking methods. We will also monitor rates of recruitment and effort required (e.g., number of staff hours), number of screenings conducted and refusal rates,² and participant lost to follow up, to inform the design of a subsequent Phased Innovation Award to Optimize Mind and Body Interventions. For refusal rate, we will ask each youth we approach their age, race/ethnicity, gender identity, and sexual orientation to allow for demographic comparisons by participation status to monitor potential sample bias. Participants will be notified that no survey data will be shared with shelter and drop-in center staff or their case workers. Data will be collected on encrypted iPads using a secured REDCap system for the baseline, follow-ups, and pre-post session surveys. This data will be collected using REDCap offline at the shelter and drop-in center in order to minimize concern over data integrity in locations with weak Wi-Fi systems. Data is stored on the hard drive of the encrypted iPad and uploaded to REDCap nightly at the UTHealth office. No data from REDCap is accessible from the iPads. The tablet will be encrypted and password protected so that no one except research staff is able to gain access to the information on the tablet and the tablet is rendered useless if stolen. Only research staff will have the passwords for the REDCap database and computer. Survey data cannot be accessed from the encrypted iPad tablet and is only accessible on the REDCap secure server. Data will be downloaded from REDCap on a weekly basis and saved on secure, firewall protected hard drives.

Pre-Post Session Survey Data. The brief pre-post session surveys will be finalized in YR-1. We anticipate measuring 'right now' measures of affect, stress, emotion regulation, and impulsivity, mindfulness, and mind wandering in the pre- and post-session surveys. We have used these items in our brief pilot of .b (manuscript under review). These brief surveys will take approximately five minutes to complete.

To assess the feasibility of proposed outcome measures we will pilot test them in the baseline and post-intervention surveys. While the surveys will be finalized during the development phase with the help of the HYWG and the Expert Advisory Panel, items will include those outlined in Table 2 and 3 in the Research Strategy.

Exit Interview. A subsample of approximately 20 participants will be asked to participate in a brief, semi-structured private or group exit interview to provide insight about the intervention and study

experience within two weeks of completing the pilot. We will randomly select and contact participants from each of the study arms ensuring that equal numbers of participants by group are selected. This will allow us to assess feasibility and acceptability of the intervention and the control condition and study procedures for all participants. The research staff, who will be trained in human subjects research methods, and trauma-informed qualitative research methods, will conduct the exit interviews using an open casual conversation style.

Example Exit Interview Guide. While the exit interview guide will be finalized during YR-1, we anticipate the RA will query the participants about: 1) what the participant thought of the number and types of questions asked in the baseline, pre-post session, and initial follow-up survey, 2) what they thought of the intervention sessions (e.g., content, length, delivery mode, frequency/spacing, perceived impact), 3) how useful the pre-programmed smartphone resource materials were (e.g., if they used it and for what), 4) utilization of smartphone apps to facilitate mindfulness practices, and 5) any other comments the participant has about the intervention or study procedures. Participants will receive a \$10 gift card for a local restaurant or grocery store for completing the exit interview.

Quality control and assurance

Data Management. The Research Coordinator will monitor study data for completeness and accuracy weekly and report to the investigative team. Ongoing training and weekly quality assurance checks will be performed to ensure adherence to confidentiality protocols. Data from the REDCap surveys will be stored on hard drives of encrypted tablets and then uploaded to a desktop microcomputer master file daily. Individual data files are automatically merged with the master data set. Weekly backups of the REDCap data set will be stored as an encrypted file and in a secure area physically remote from the data management area. All study related forms, surveys, and data will be destroyed by shredding after seven years. All necessary firewall and password protections will be implemented to restrict access and ensure data confidentiality.

Role of the Data Safety Monitoring Board. A monitoring board will review the data monitoring and safety procedures annually. This group will comprise 3 members with expertise in risk prevention, health communication, and/or homeless youth intervention research. [name] at the University of Texas Medical Branch; [name] at the University of California San Francisco Center for AIDS Prevention Studies; and [name] at the UTHealth School of Public Health will be the monitoring board members. Monitoring board meetings will be conducted annually, beginning after the first 6 months of data collection. In addition, should any adverse reaction occur, the monitoring board will be informed immediately, and a special session will be scheduled to discuss strategies to deal with the problems. The meeting will include a synopsis of protocol and design, discussion of the status of interventions and data collection procedures, a summary of subject contacts, discussion of any adverse reactions or potential adverse reactions, status of data entry and verification, and a summary of any descriptive and inferential statistics to date. However, data analyses will be conducted on each time point of data collection (baseline, immediate, 3- and 6-months post-intervention) as it is completed. In addition, the monitoring board will be given time to meet in closed session without the investigators to discuss the need for additional procedures to prevent adverse reactions or ensure data integrity or the unlikely case that the study may need an early termination due to unexpected adverse reactions or inadequate conduct of the study. Recommendations from the monitoring board meetings will be shared with the UTHealth IRB and NIH during annual reports and immediately if the monitoring board identifies adverse reactions not previously reported or recommends early termination of the study.

Publication Plan

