Examining the feasibility and acceptability of a tailored version of a Mindfulness-Based Intervention (MBI) among YEH aged 18-25 years old

NCT04950816

Version Date: 01/15/2025

Refer to page 16, for the pilot study (Aim 3) registered as ClinicalTrials.gov record NCT04950816.

Protocol Title:	Examining the feasibility and acceptability of a tailored version of a Mindfulness-Based Intervention (MBI) among YEH aged 18-25 years old
Principal Investigator:	[name] [name], RN
Co-Investigators:	[name], [name], MHS, [name], MSW
Study Coordinator:	[name]
Population:	Homeless Youth Focus groups (n=56) Homeless Youth Working group (n=10) Pilot RCT with Youth Experiencing Homelessness ages 18-25 (n=90) Total of 156 Youth Experiencing Homelessness ages 18-25 in Houston, TX
Number of Sites:	Single site
Study Duration:	Three (3) years
Subject Duration:	Six (6) months for subjects in pilot RCT

General Information

This proposed development and pilot study will examine the feasibility and acceptability of a tailored version of a Mindfulness-Based Intervention (MBI), .b, among (Youth Experiencing Homelessness) YEH aged 18-25 years old. Building on our promising pilot research, we will work with YEH to tailor .b, including ensuring a trauma-informed approach. Using iterative beta testing with a (Homeless Youth Working Group) HYWG, we will tailor the intervention and determine appropriate methods and strategies for recruitment, adherence, and retention. Finally, we will conduct an attention control RCT pilot study of the tailored version of .b to determine feasibility and acceptability of conducting an adequately-powered RCT. We will test our recruitment/retention methods, enrollment criteria, randomization protocol, participant tracking and follow-up processes, and study measures. With the pilot, we will determine whether participants will adhere to the intervention protocol (i.e., attend sessions, complete study measures). We will determine whether the enrollment criteria appropriately identify and exclude youth who cannot safely participate in the study and if our tracking and follow-up protocol is feasible and acceptable. The results of the pilot will inform the sample size needed for a fully powered, attention control RCT of the tailored .b to provide robust and clinically useful data on intervention efficacy among YEH.

Background Information

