Innovation. This proposal will be the first to use participatory research strategies to tailor and pilot test an MBI for sheltered YEH. This study is based on a strong scientific premise supporting the high rates of stress and the positive impact of mindfulness strategies on stress management skills, emotion regulation, and impulsivity. This study is innovative because 1) we are engaging this vulnerable population in participatory, community-engaged research strategies to tailor an evidence based MBI (.b), 2) we are using cognitive interviewing to validate outcome measures, and 3) we will test the acceptability of commercially available mindfulness apps and determine the optimal measure of app use. Data usage information will be gathered from mediation app on participants' phone .The iterative pre-piloting approach we propose to use in this study will allow our team to quickly respond to user feedback to adjust intervention content, delivery methods, and outcome measures to assure a rigorous pilot. Our team of interprofessional experts in public health nursing, adolescent medicine, child development, social work science, and mindfulness instruction and research has worked extensively with YEH on observational, longitudinal, and intervention studies and among other at-risk youth and vulnerable young adult populations using MBIs (see biosketches). Our extensive preliminary work builds on findings from mindfulness experts and demonstrates promising outcomes of MBIs among YEH while highlighting the need for programs to be trauma-informed and tailored to enhance relevance and efficacy and scalability to a sheltered population of YEH.

Planning for a Randomized Trial. To conduct a rigorous RCT of an MBI for YEH, several essential aims need to be completed that this R34 will address. **First**, while evidence is mounting that MBIs may be effective, and MBIs have been tested among YEH, no MBIs has been specifically tailored for sheltered YEH. While .b has the main components that show promise, modifications are needed to assure cultural and situational relevance for YEH. **Second**, the control condition needs to be optimized to assure smooth trial implementation. **Third**, outcome measures and follow-up protocols need to be optimized. **Finally**, a test of feasibility for conducting a small RCT with longer participant follow-up is needed to inform the R01 protocol, measures, and sample size needed.

Objectives

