This study is *significant* as it lays the groundwork for a potentially beneficial program for YEH, a vulnerable, high risk, and growing population by tailoring and testing an intervention that targets the root causes of many health risk behaviors. If effective, the intervention has the potential to have far-reaching effects on youths' health and wellbeing. This scientific premise builds on the substantial body of literature that demonstrates the link between trauma, stress, maladaptive decision making, and risk behaviors and the promising effects of MBIs in high-risk youth. This *innovative* study capitalizes on established relationships with local providers and our access to this difficult-to-reach population to collaborate on tailoring of *.b* for a sheltered sample of YEH. This research aligns with NCCIH Priority Research Areas by developing and feasibility testing of a tailored MBI and evaluating its overall health and wellness impact. Data from this R34 will inform the development of an adequately-powered RCT, optimizing the recruitment and retention strategies, informing the final sample size for a larger randomized trial, and finalizing the outcome measures needed.

Study Design

This proposed study will fully develop and pilot test the feasibility and acceptability of a tailored mindfulness-based intervention among young adults experiencing homelessness ages 18-25 years old. The intervention targets stress management, emotion regulation, and impulsivity. A total of 56 homeless youth will participate in the focus group discussions (FGDs), 10 youth per session will participate and study team will consent up to 30 homeless youth for the Homeless Youth Working Group (HYWG) to account for participant drop off, 12 health and social services providers will participate in the key informant interviews, 8 service providers and 2 youth will participate on the Expert Advisory Panel (EAP), and 90 homeless youth will participate in the randomized attention control pilot study.

Expected duration of study and subject participation. Study duration is 3 years and subjects in the pilot RCT will be in the study for 6 months. Key informants and Homeless Youth Working Group will be part of the study for one year. The expert advisory panel will be in the study all three years.

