Role of NIH. Summaries of the protocol and design, status of intervention group, and data collection procedures, summary of subject contacts, discussion of any adverse reactions or any potential adverse reactions, status of data entry and verification, a summary of any descriptive statistics to date, and the recommendations of the monitoring board will be included in each annual report to NIH. In addition, should any adverse reaction occur or should the monitoring board recommend early termination of the study, the information will be immediately reported to the program officer at NCCIH.

Statistics

Fifty six YEH will participate in the focus groups during the first 2 years of the study to Tailor .b and finalize the attention control condition. Sixty YEH will participate in the pilot RCT.

Sample Size for Pilot RCT. We will recruit 90 YEH with equal randomization into the intervention and attention control arms to reach the target of 60 YEH completing the intervention and control conditions. The sample size is based on practical considerations regarding the number of participants needed to assess feasibility and acceptability outcomes and not on the performance of inferential statistical analyses. However, a final sample size of 60 youth completing the pilot will have 80% power to detect a medium effect size of 0.74 for stress response.¹⁸²

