Data Management and Statistical Analysis Plan. To align with the R34, we will not conduct inferential statistical analyses. The analyses goal is to examine study feasibility and acceptability, determine effectiveness of recruitment and randomization strategies, follow-up and retention protocols, and preliminary assessment of outcome measures using both quantitative and qualitative methods (See Table 3). In summary, for the quantitative analyses, frequencies and percentages will be calculated to determine the recruitment, retention, attendance, and data collection rates (See Table 3). While we do not anticipate missing data based on the low rate of missingness in our previous work using similar surveys and data collection methods, we will assess for and calculate the rates of missing and incomplete data to inform future studies. Means and standard deviations will be used to summarize changes in the outcome variables over the three time points (e.g., baseline, immediate post-intervention, and at 3- and 6-months). Estimation of effect sizes due to the intervention will involve the use of one-way repeated measures analysis of variance to provide the effect size R² for each proposed outcome variable.

For the qualitative analyses, we will analyze the data from FGDs, key informant, and exit interviews using thematic content analysis.^{174,183} Audio files will be transcribed and validated against the written transcriptions. For the initial set of 2 FGDs and 5 interviews, the qualitatively trained RA will review the text for content and identify 5-10 themes. Next, we will develop a codebook through preliminary discussions of themes and team coding among the study team and refine the codebook iteratively with the HYWG and EAP to form a final set of codes. Then, two investigative team raters (Drs. [name] and [name]) will independently categorize passages until excellent interrater reliability (Cohen's kappa (k) = .85) is achieved. A thematic content analysis will be conducted to look for common themes present across the entire sample. The investigative team will discuss emerging themes and subthemes with the HYWG and EAP to generate the final results. ATLAS.ti will be used to manage the data, organize codes, and exemplar quotes. The team will meet to review coded data and discuss the meaning of the themes

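### The pilot is to inform the full trial's sample size, but its only effect output is R² without an interval, and nothing says the full trial will not be sized on it

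*Combined protocol and SAP*

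**What the plan says.** Three places give the pilot a role in designing the next trial. General Information states: "The results of the pilot will inform the sample size needed for a fully powered, attention control RCT". Planning for a Randomized Trial says that a small RCT with longer follow-up "is needed to inform the R01 protocol, measures, and sample size needed". The significance paragraph under Objectives lists "informing the final sample size for a larger randomized trial, and finalizing the outcome measures needed". None of them says which pilot outputs will be used, or how.

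Under Statistics, the Sample Size for Pilot RCT paragraph reads "We will recruit 90 YEH with equal randomization into the intervention and attention control arms" and continues "to reach the target of 60 YEH completing the intervention and control conditions". It calls this number practical rather than inferential, then adds that 60 completers give "80% power to detect a medium effect size of 0.74 for stress response". The Data Management and Statistical Analysis Plan rules out inferential analysis. On effects it says: "Estimation of effect sizes due to the intervention will involve the use of one-way repeated measures analysis of variance", with R² as the reported quantity for each proposed outcome. No confidence interval is planned for this or any other quantity. The same section also plans means and SDs of the outcomes, rates of recruitment, retention, attendance and data collection, and rates of missing data.

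For the measures, Aim 2 and its Cognitive Interviews paragraph name understandability and participant burden. Aim 3b names feasibility, and Table 3 has a benchmark for completeness of assessment data.

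**The concern.** A sample-size calculation needs a target difference. The documents name none for the full trial, and no smallest worthwhile effect appears anywhere. The pilot's R² is the only effect figure the analysis plan will produce, so it is the figure closest to hand when the next application is written. Without an interval, nothing beside it shows how weak a basis it is.

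The consequences would fall on the next trial. A chance high estimate would give a trial too small to detect the true effect. A chance low one could lead the team to drop a useful programme. Both matter in a population that is hard to recruit and follow.

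**Working it through.** **Inputs.** From Sample Size for Pilot RCT: 90 randomised equally, 60 completing (30 per arm), effect 0.74, power 80%. From Table 3: at least 50% retained at 3 and 6 months, so 0.50 × 90 = 45 youth (22.5 per arm on average). Assumed, because not stated: two-sided alpha 0.05, SD of 1 (so that 0.74 is Cohen's d), and true d of 0.2 to 0.5.

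**1. The plan's own figure.** Power = Φ(d/√(2/n) − 1.960). With d = 0.74 and n = 30: 0.74/0.2582 = 2.866, and Φ(0.906) = 81.8%. The noncentral t gives 80.5%, and the detectable d at 80% power is 0.736. The stated 80% reproduces.

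**2. Precision of a between-arm d.** SE(d) = √(2/n + d²/(4n)), here at d = 0.3.
- 60 youth: √(0.0667 + 0.0008) = 0.260; × 1.96 = 0.51.
- 45 youth: √(0.0889 + 0.0010) = 0.300; × 1.96 = 0.59.
- Delivery in groups of about 10 could widen this. With an assumed intraclass correlation of 0.05 or 0.10, the half-width at 60 youth is 0.61 or 0.70.

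**3. What an estimate would imply.** Noncentral-t intervals at 30 per arm, with full-trial size per arm = 2(1.960 + 0.842)²/d² for 80% power:

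| Observed d | 95% CI | Total N at the estimate | Total N across the CI |
|---|---|---|---|
| 0.30 | −0.21 to 0.81 | 350 | 50 to no finite N |
| 0.50 | −0.02 to 1.01 | 126 | 32 to no finite N |
| 0.74 | 0.21 to 1.26 | 58 | 20 to 690 |

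R² hides this. For two equal arms R² = d²/(d² + 4), so d = 0.3 corresponds to R² = 0.022, while the average R² with no effect at all and 60 youth is 1/59 = 0.017.

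**4. If the full trial were sized on the estimate.** Let e be the pilot estimate, normal with mean d and SE √(2/30) = 0.258. A trial sized for 80% power at e has true power Φ(2.802 × d/e − 1.960), which is below 80% exactly when e exceeds d. Suppose the team proceeds only if e exceeds a cut c. Then P(power < 80%) = 0.5/P(e > c), and median power is found at the median of e above c.

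For d = 0.3:
- c = 0: P(e > 0) = 0.877 and 0.5/0.877 = 57%. Median e = 0.340; Φ(2.802 × 0.3/0.340 − 1.960) = Φ(0.51) = 70%.
- c = 0.1: P(e > 0.1) = 0.781 and 0.5/0.781 = 64%. Median e = 0.372; Φ(0.30) = 62%.

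At the ends of the assumed range:
- d = 0.2, c = 0.1: median e = 0.317; Φ(2.802 × 0.2/0.317 − 1.960) = Φ(−0.19), about 42%.
- d = 0.5, c = 0: median e = 0.509; Φ(2.802 × 0.5/0.509 − 1.960) = Φ(0.79), about 79%.

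**5. Outputs that are usable.** With 60 youth, the 95% interval for an SD is 0.85 to 1.22 times its estimate. If 60 of 90 are retained, the exact interval for retention is 56% to 76%. These are far better inputs to a sample-size calculation than the effect estimate.

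**The case against.** The strongest reply is that the documents say the pilot informs the sample size, not that its effect estimate fixes it. SDs, retention and attendance also inform a sample size, and all are planned. The pilot is described as practical in size and non-inferential, and Next Steps puts efficacy in later trials, after more feasibility and dose work. On this view, step 4 models a procedure nobody has proposed, and any harm lies in a future protocol with its own review.

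Much of this stands, and it rules out four stronger readings a reader might infer:
- That the full trial's size will be computed from the pilot effect. No section says so; the gap is that none excludes it.
- That the pilot yields nothing but effect sizes. The analysis plan lists the other outputs set out above.
- That measures will be picked because their pilot effects were largest. The stated criteria are understandability, burden, feasibility and completeness. Selection on effect size is a risk left open at the final choice, not a plan.
- That 30 per arm cannot tell no effect from a large one. Power is 86% at d = 0.8 and 80.5% at 0.74, and an observed 0.74 has an interval that excludes zero. The difficulty is with small-to-moderate effects.

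The reply does not supply a target difference, an interval, or a sentence keeping the pilot effect out of the calculation.

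**Conclusion.** The concern holds as a gap in the plan. The pilot is meant to inform the size of the full trial, yet its one effect output carries no measure of precision, and the documents leave open whether it will become the planning effect. The half-widths in step 2 depend only on the stated numbers, with equal arms and no clustering by session group. The power figures are conditional: they apply only if the trial is sized on the estimate, and they rest on the assumed true d. Across assumed values of 0.2 to 0.5, median power runs from about 42% to 79%, so the size of the loss varies, but the median stays below the intended 80% throughout. The pilot's feasibility and acceptability conclusions are not affected. The change is worth making because it is cheap and protects the product the pilot is meant to deliver.

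**What to change.** 1. In the Data Management and Statistical Analysis Plan, report for each outcome a between-arm effect size with a 95% confidence interval, labelled descriptive. This fits the decision not to test hypotheses. Naming the between-arm contrast matters because a one-way repeated measures analysis, as worded, specifies no group-by-time term, so its R² may not compare the arms.
2. In General Information, Planning for a Randomized Trial and Objectives, state that the full trial's target difference will be a worthwhile difference fixed beforehand, and that the pilot will supply the SDs, retention and attendance already planned.
3. Beside the statement about finalizing measures, add that observed effect size will not be used in the final choice. The existing criteria can stay as they are.

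The cost is a few sentences and one extra table column. The real concession is that the team gives up quoting the pilot effect as the planning effect in its next application.
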